**Secondary Endpoints:**

- Modulation of systemic hormones, growth factors, and cytokines (insulin, sex steroid hormone, IGF-axis, adipokines) and anthropometric measures
- Modulation of metabolomic profiles in NAF and plasma and correlations of metabolomic profiles with markers of breast cancer risk

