### **Secondary objectives:**

- To determine the effect of metformin intervention on metabolic disturbances and body weight/composition. Changes in circulating levels of insulin, IGF axis, sex steroid hormones, adipokines, and anthropometric measures will be assessed and compared between treatment groups.
- To explore the application of metabolomics as a systems biology approach to assess the chemopreventive mechanisms of metformin. The global profiles of biochemicals and metabolites in nipple aspirate fluid (NAF) and plasma will be assessed through unbiased metabolome wide analysis to determine the metabolic changes induced by metformin in comparison with placebo. We will also explore whether metformin-induced metabolic changes correlate with metformin-induced changes in markers of breast cancer risk or side effects. In a cross-sectional fashion, we will explore the correlations between baseline metabolic features with breast density and circulating levels of hormones and cytokines.

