For the metabolomic aim, pre- to post-intervention changes in all detectable compounds of known identity (currently comprising 397 biochemicals using the standard platforms offered by Metabolon, Inc) will be determined and compared between treatment groups using a two-sample t-test. An estimate of the false discovery rate ( $q$ -value) will be calculated (115) to take into account the multiple comparisons that normally occur in metabolomic-based studies. A low  $q$ -value ( $q \leq 0.10$ ) is an indication of high confidence in a result. While a higher  $q$ -value indicates diminished confidence, it does not necessarily rule out the significance of a result. Other lines of evidence may be taken into consideration when determining whether a result merits further scrutiny. Such evidence may include a) significance in another dimension of the study, b) inclusion in a common pathway with a highly significant compound, or c) residing in a similar functional biochemical family with other significant compounds.

Exploratory analyses will assess whether the observed metformin-induced changes in metabolite features are correlated with changes in FWR-MRI, body weight/composition, systemic hormones, and cytokines. The correlation will be estimated using a Pearson correlation coefficient. It is expected that any changes in these variables in the placebo group will reflect random variation only. Thus, these analyses will be restricted to the metformin group to overcome dilution of the potential correlations by individuals in the placebo group.

Exploratory analyses also will explore the correlation between baseline metabolite features and FWR-MRI, systemic hormones, and cytokines. These analyses will be restricted to

the metabolite features that are members of a common pathway to reduce the potential for an inflated alpha level.

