### **9.2 Sample Size Justification**

Our sample size ensures adequate power to test all primary specific aims. We assume an initial sample size of 75 women per arm and allow the possibility of up to 20% dropout for the 12-month follow-up measurement. This results in at least 60 evaluable women per group. To justify the sample size, we use the simplified comparison of change between 12 months versus baseline (ignoring the 6 month measurement). For the FWR-MRI-derived change in breast density, we will be able to detect a decrease of 0.516 standard deviation (SD) units in the metformin treated women with 80% statistical power, assuming a two-sided  $\alpha$  of 0.05. To estimate what this change would be in relation to breast density, we used the relationship between breast density and  $\log(\text{Fra50})$  based on our previous data. Based on an analysis of our cross-sectional data, the estimated SD of  $\log(\text{Fra50})$  is 2.40. Thus, a decrease of 0.516 SD units corresponds to a change of  $-1.2384$  ( $-0.516 \times 2.40$ ). Based on the regression line, this is equivalent to a 10% decrease in breast density as determined by standard mammography. For the additional primary outcomes (such as systemic hormones, cytokines, and weight), we will be able to detect a difference of 0.516 SD units with 80% statistical power, assuming a sample size of 60 evaluable women per group. Based on our previous experience, we anticipate that 65% of the proposed cohort will provide sufficient NAF for metabolomic analysis, which results in 39 women per group (allowing for up to 20% drop-out). This will allow us to detect a difference of 0.643 SD units with 80% statistical power.

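### The 80% power stated for NAF metabolomics is per compound at an unadjusted two-sided 0.05; at the plan's own q ≤ 0.10 mark it is lower unless roughly a third or more of the compounds change

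*Combined protocol and SAP*

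**What the plan says.** Section 9.2 (Sample Size Justification) starts from 75 women per arm and 20% dropout. For NAF it states that "we anticipate that 65% of the proposed cohort will provide sufficient NAF for metabolomic analysis, which results in 39 women per group", and then: "This will allow us to detect a difference of 0.643 SD units with 80% statistical power". That sentence names no alpha, no number of compounds and no q-value. The only alpha in 9.2 comes earlier in the same paragraph, for the MRI breast density endpoint: "in the metformin treated women with 80% statistical power, assuming a two-sided" level of 0.05.

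Section 9.1 (Analysis Plan) describes the analysis that this power is meant to support. The pre- to post-intervention change in every detectable known compound ("currently comprising 397 biochemicals using the standard platforms offered by Metabolon, Inc") is compared between arms by a two-sample t-test, and q-values are calculated because of the multiple comparisons. A q-value of 0.10 or less "is an indication of high confidence in a result". Of a higher q-value the plan says "it does not necessarily rule out the significance of a result", and it lists other kinds of evidence that may count.

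On status, the Schema lists among the secondary endpoints "Modulation of metabolomic profiles in NAF and plasma and correlations of metabolomic profiles with markers of breast cancer risk", while the secondary objectives in section 1 word the aim as "To explore the application of metabolomics as a systems biology approach to assess the chemopreventive mechanisms of metformin".

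**The concern.** The stated power and the planned analysis use different yardsticks. The power belongs to one t-test judged at p ≤ 0.05. The analysis runs about 397 such tests and attaches high confidence to q ≤ 0.10, which usually demands a much smaller p-value. It demands less only when a large share of the compounds truly changes.

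The 80% is the only power figure given for the NAF comparison. A reader may take it as the chance that a real change of 0.643 SD appears on the high-confidence list. If that chance is nearer one half, a short list of compounds could be misread as little effect of metformin in the breast when it partly reflects limited power.

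**Working it through.** **Inputs from the documents.** Section 9.2: 75 per arm, 20% dropout, 65% NAF yield, 0.643 SD, 80% power, two-sided 0.05 (stated for the MRI endpoint). Section 9.1: two-sample t-test per compound, 397 compounds, q ≤ 0.10.

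**Assumptions, not in the documents.** The share *s* of compounds that truly change; the size of their shifts; independence between compounds; q-values that use an estimate of the share of unchanged compounds.

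**Step 1: the plan's own figure.** 75 × 0.80 × 0.65 = 39 per group. The noncentral t with 76 degrees of freedom and noncentrality d × √(39/2), at two-sided 0.05, gives 80% power at d = 0.6426; power at 0.643 is 80.05%. One-sided 0.05 would give 0.568, and 0.05/397 would give 1.113. The same method with 60 per group gives 0.516, the other figure in 9.2. So the NAF figure is unadjusted two-sided 0.05. That alpha is inferred, but no other variant tried fits.

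**Step 2: p ≤ 0.05 set against q ≤ 0.10.** The false discovery rate at p ≤ 0.05 is (1 − s) × 0.05 / [(1 − s) × 0.05 + s × 0.80].
- s = 5%: 0.0475 / (0.0475 + 0.0400) = 54%
- s = 10%: 0.0450 / (0.0450 + 0.0800) = 36%
- s = 20%: 0.0400 / (0.0400 + 0.1600) = 20%

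**Step 3: power at q ≤ 0.10, all changed compounds at 0.643 SD.** The p-value cut-off t solves t = 0.10 × s × P(t) / [0.90 × (1 − s)], where P(t) is the t-test power at cut-off t.

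| Share changed | Cut-off t | Average power |
|---|---|---|
| 5% | 0.0022 | 38% |
| 10% | 0.0064 | 52% |
| 20% | 0.0185 | 67% |
| 36% | 0.0500 | 80% |

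Check at 10%: 0.10 × 0.10 × 0.517 / (0.90 × 0.90) = 0.0064. Simulation of 397 independent t-tests with estimated q-values (400 runs per scenario) gave 41%, 53%, 67% and 80%. In a separate simulation with correlated blocks (correlation 0.5), mean power was 39%, 51% and 66% at 5%, 10% and 20%.

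**Step 4: share needed for 80% at 0.643 SD.** The cut-off must be 0.05, so s/(1 − s) = 0.05 × 0.90 / (0.10 × P) = 0.45/P, where P is the average power over all changed compounds at p ≤ 0.05. Single-compound power at that cut-off is 0.258 for 0.3 SD, 0.800 for 0.643 SD and 0.992 for 1.0 SD.
- All at 0.643 SD: P = 0.800, odds 0.562, s = 36% (about 143 of 397)
- Half at 1.0 SD: P = 0.896, odds 0.502, s = 33%
- Half at 0.3 SD: P = 0.529, odds 0.850, s = 46%
- Three quarters at 0.3 SD: P = 0.393, odds 1.144, s = 53%
- Nine tenths at 0.3 SD: P = 0.312, odds 1.442, s = 59%

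**Step 5: difference detectable with 80% average power at q ≤ 0.10.** Setting P = 0.80 gives cut-offs of 0.0047, 0.0099, 0.0222 and 0.0500 at 5%, 10%, 20% and 36% changed. With 39 per group these correspond to 0.854, 0.792, 0.721 and 0.643 SD.

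**The case against.** The best defence is that nothing in 9.2 is false. The planned test is a t-test per compound, 0.643 SD is exactly the power of that test, two-sided 0.05 stands in the same paragraph, and 9.2 never claims 80% power at q ≤ 0.10. This stands against any charge of miscalculation: what is missing is a label. It does not remove the need for one, because 9.1 gives its only numerical mark on a different scale.

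Second, q ≤ 0.10 is not a decision rule. Section 9.1 lets a compound with a higher q-value be pursued on other evidence, and the aim is worded as exploration. Both points stand and lower the weight. Even so, NAF profiles are also listed as a secondary endpoint, and the plan chose to state a power for them; a stated power should say what it refers to.

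Third, the share of changing compounds is unknown. That is true, and it is why only scenarios can be given.

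Some stronger readings are tempting but unsupported:
- *The NAF aim is underpowered.* The documents give no expected share, so actual power at q ≤ 0.10 cannot be fixed.
- *The trial's size is wrong.* Section 9.2 builds the sample size on 60 evaluable women per group; the NAF number follows from that and did not set it. The primary endpoint is untouched.
- *There is a definite upper limit on the share needed.* There is none: it rises as more of the changed compounds shift only slightly.
- *The same gap applies to plasma.* Section 9.2 gives no separate plasma metabolomics figure. If all 60 completers per arm gave plasma (an assumption), power at 0.643 SD would be about 73% at 5% changed and 82% at 10%.

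**Conclusion.** The concern holds as a mismatch between the stated power and the planned analysis. It is not an arithmetic error. The 0.643 SD figure is certain as a per-compound calculation at unadjusted two-sided 0.05. At q ≤ 0.10, average power for that difference is about 38% to 67% if 5% to 20% of compounds change. It reaches 80% only at about 36% if all changed compounds shift by 0.643 SD, and at 46% or 53% if half or three quarters of them shift by just 0.3 SD. A somewhat smaller share, about 33%, is enough if half shift by 1.0 SD.

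The q ≤ 0.10 values are approximate. They rest on independent compounds, the effect sizes shown and q-values that estimate the unchanged share; without that estimate (Benjamini-Hochberg) the common-effect share needed would be about 60% instead of 36%. The practical weight is limited because the mark is a guide and the aim is exploratory. The sentence should still be corrected, because it is the only power statement for this endpoint.

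**What to change.** In 9.2, replace the NAF power sentence with text such as: *With 39 women per group, a difference of 0.643 SD is detectable with 80% power per compound (two-sided 0.05, unadjusted for multiplicity). At q ≤ 0.10, the difference detectable with 80% average power is about 0.85, 0.79, 0.72 and 0.64 SD if 5%, 10%, 20% and 36% of compounds change. These values are approximate and assume independent compounds and a common effect size; q ≤ 0.10 is a mark of confidence, not a strict cut-off.*

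The label in the first sentence is the essential part. The 20% value should be given as 0.72 and not rounded to 0.7, since average power at 0.70 SD is only 76.9%.

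The cost is a few lines in 9.2. Sample size, test, q-value threshold and analysis do not change. The only downside is a less favourable stated figure.

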### **9.3 Interim Analysis**

No formal interim statistical analyses are planned for this Phase II trial. Accrual, data collection, and any adverse events will be monitored on a regular basis.

## **10. Data and Safety Monitoring Plan**

### **10.1 Protocol Risk Level**

This trial has been designated as a medium risk study. Medium risk studies are intended to include all trials involving therapeutic intervention(s), which are not designated as high risk per NCI and the IND is not held by the investigator.

### **10.2 Identification of the DSMB Obligated for Oversight Responsibilities**

The University of Arizona Cancer Center Data and Safety Monitoring Board (DSMB) will provide ongoing oversight for this trial semi-annually.

### **10.3 Identification of the Entity Obligated for Routine Monitoring Duties**

Routine monitoring will be provided by the Quality Assurance/Quality Control (QA/QC) Program to ensure that the investigation is conducted according to protocol design and regulatory requirements.

### **10.4 Monitoring Progress and Data Review Process**

Routine monitoring of participant data will be conducted at least every 6 months.

The first routine monitoring visit will include at a minimum:

- Informed consent – 100% of cases enrolled;
- Participant eligibility - 50% of cases, up to two participants;
- Data review - 50% of cases, up to two participants.

All subsequent monitoring visits will consist of randomly selected participant cases based on current enrollment and include continuing review of previously selected cases, as applicable. A monitoring visit report and follow-up letter will be completed within approximately

two weeks of the routine monitoring visit; a copy will be maintained in the study file. A query/finding form or an electronic record will also be completed by the monitor to request additional source documentation, clarification, information or corrections to the CRF and/or regulatory records. The study coordinator or other applicable staff responsible for the study will be given a copy of this form or will be notified of the electronic record for resolution of queries/findings. The query/finding form will be maintained with a copy of the visit report for follow-up at the next monitoring visit.

The Principal Investigator will ensure the accuracy, completeness, legibility and timeliness of the data reported in the Case Report Form (CRF), or other acceptable data formats. Source documentation supporting the study data should indicate the participant's participation in the trial and should document the dates and details of study procedures, adverse events, and participant status. CRFs should be completed via the institutional database or other acceptable data formats. Trials using paper CRFs will have data entered with a black ball-point pen or typed. Corrections to the forms should not obscure the original entry and should be made by striking the incorrect information with a single line. Each strike should be accompanied by the initials of the corrector and the correction date. All participant forms and study files will be stored in a secure area limited to authorized staff. **Note:** Routine monitoring of regulatory documents and test article will be conducted at least annually. A process is in place to implement study closure when significant risks or benefits are identified.

## 11. Description and Reporting of Adverse Events

### 11.1 Adverse Events

An adverse event (AE) is any untoward medical occurrence in a study participant. An AE does not necessarily have a causal relationship with the treatment or study participant. An AE can therefore be any unfavorable and unintended sign (including a clinically significant abnormal laboratory finding), symptom, or disease temporally associated with participation in a study, whether or not related to that participation. This includes all deaths that occur while a participant is on a study.

A list of adverse events that have occurred or might occur (Reported Adverse Events and Potential Risks) can be found in Section 6.2, Pharmaceutical Information as well as the package insert.

All adverse events that occur after the informed consent is signed must be recorded whether or not related to study agent. All adverse events will be entered into the OnCore database.

AE Data Elements include:

- AE reported date
- AE Verbatim Term
- Common Terminology Criteria for Adverse Events v4.0 (CTCAE) AE term
- Event onset date and event ended date
- Severity grade
- Attribution to study agent (relatedness)
- Whether or not the event was reported as a Serious Adverse Event (SAE)
- Whether or not the subject dropped due to the event
- Action taken with the study agent
- Outcome of the event
- Comments

All AEs will be assessed according to CTCAE Version 4  
 (<http://ctep.cancer.gov/protocolDevelopment/electronicapplications/docs/ctcaeV4.pdf>).

AEs that do not have a corresponding CTCAE term will be assessed according to the general guidelines for grading used in the CTCAE v4.0 as stated below.

Grade	Severity	Description
1	Mild	Mild; asymptomatic or mild symptoms; clinical or diagnostic observations only; intervention not indicated.
2	Moderate	Moderate; minimal, local or noninvasive intervention indicated; limiting age-appropriate instrumental ADL*.
3	Severe	Severe or medically significant but not immediately life-threatening; hospitalization or prolongation of hospitalization indicated; disabling; limiting self care ADL**.
4	Life threatening	Life-threatening consequences; urgent intervention indicated.
5	Fatal	Death related to AE.

Activities of Daily Living (ADL)

\*Instrumental ADL refer to preparing meals, shopping for groceries or clothes, using the telephone, managing money, etc.

\*\*Self care ADL refer to bathing, dressing and undressing, feeding self, using the toilet, taking medications, and not bedridden.

The possibility that the adverse event is related to study agent will be classified as one of the following: not related, unlikely, possible, probable, definite.

All AEs, including lab abnormalities that in the opinion of the investigator are clinically significant, will be followed according to good medical practices and documented as such.

### 11.2 Serious Adverse Events

ICH Guideline E2A and Fed. Reg. 75, Sept. 29, 2010 define serious adverse events as those events, occurring at any dose, which meet any of the following criteria:

- Results in death
- Is life threatening (*Note: the term life-threatening refers to an event in which the patient was at risk of death at the time of the event; it does not refer to an event which hypothetically might have caused death if it were more severe*).
- Requires inpatient hospitalization or prolongation of existing hospitalization
- Results in persistent or significant incapacity or substantial disruption of the ability to conduct normal life functions.
- Is a congenital abnormality/birth defect
- Important medical events that may not result in death, be life-threatening or require hospitalization may be considered serious when, based upon appropriate medical judgment, they may jeopardize the patient or subject and may require medical or surgical intervention to prevent one of the outcomes listed.

**Note:** A SAE may also be an important medical event, in the view of the investigator that requires medical or surgical intervention to prevent one of the outcomes listed above.

All serious adverse events, regardless of attribution, and any deaths will be reported within 24 hours of notification of the event to the DSMB Coordinator. All SAEs which meet the criteria for a reportable event, as defined below, will be reported to the University of Arizona Human Subjects Protection Program (HSPP) within 10 working days of the event date or receipt of notification of the event.

Reportable events must meet all three of the following criteria:

- Unanticipated or unexpected in nature, frequency or severity, AND
- Related or possibly related to participation in the research (there is a reasonable possibility that it is related), AND
- The event suggests that the research places participants or others at a greater risk of harm than was previously known or recognized (not already referenced in existing study documents, such as the protocol, consent form or package insert).

All serious adverse events will be processed by the DSMB Coordinator monthly for initial trend analysis and fully reviewed by the DSMB, every six months. The DSMB coordinator will review the SAE reporting process to confirm reporting requirements are met.

### **11.3 Plan for assuring data accuracy and protocol compliance**

Routine study activity and safety information will be reported to the DSMB every six months, or more frequently if requested. These reports will include:

- Study activity, cumulative and for the period under review;
- Safety (narrative description on non-serious and serious adverse events);
- Predetermined protocol early stopping rules for efficacy/futility;
- Monitoring and protocol compliance;
- Comments;
- Attachments (AE data reviewed by the PI to compile the report, SAE letters and reports, results of any review(s), applicable correspondence with the HSPP or other regulatory agencies).

Data, safety and study progress will be reported to HSPP at least annually and funding agency, as applicable. The PI will immediately notify, in writing, the funding agency, if applicable, any action resulting in a temporary or permanent suspension of the study.

### **11.4 Process to implement study closure when significant risks or benefits are identified**

There will be no formal stopping criteria. However, if periodic review performed by the UACC DSMB identified patterns of significant risks, a discussion of more frequent monitoring or early closure will be conducted between DSMB and the investigators.

## **12. Regulatory Considerations**

### **12.1 Regulatory Board Review**

The study protocol will be activated after review and approval by the University of Arizona Cancer Center Scientific Review Committee and the University of Arizona HSPP. Approval of this protocol by the HSPP will also include approval of the protocol consenting document, or Informed Consent Form (ICF) and the accompanying HIPAA consenting instrument.

### **12.2 Compliance with Protocol and Protocol Revisions**

Study personnel will conduct the study as described in this protocol. Any protocol revisions made in amendments to the protocol will be approved by the HSPP prior to implementation, except where necessary to avoid imminent hazard to a study participant. If an amendment alters the study design or increases the potential risk to the participant, the ICF will be revised and submitted for approval to the HSPP. The revised ICF will be used to obtain consent from participants currently enrolled in the study or after withdrawal from the study if they are affected by the Amendment.

